8.4.5 Pregnancy and Exposure During Breastfeeding

Although pregnancy and infant exposure during breastfeeding are not considered AEs, any pregnancy or infant exposure during breastfeeding (spontaneously reported to the investigator or their designee) that occurs in a participant during the study are reportable to the Sponsor.

All reported pregnancies must be followed to the completion/termination of the pregnancy.

Any pregnancy complication will be reported as an AE or SAE.

The medical reason (example: maternal health or fetal disease) for an elective termination of a pregnancy will be reported as an AE or SAE. Prenatal testing showing fetus will be born with severe abnormalities/congenital anomalies that leads to an elective termination of a pregnancy will be reported as an SAE for the fetus.

Pregnancy outcomes of ectopic pregnancy, spontaneous abortion, missed abortion, benign hydatidiform mole, blighted ovum, fetal death, intrauterine death, miscarriage, and stillbirth must be reported as serious events (Important Medical Events). If the pregnancy continues to term, the outcome (health of infant) must also be reported.

8.4.6 Disease-related Events and/or Disease-related Outcomes Not Qualifying as AEs or SAEs

Not applicable for this study.

8.4.7 Events of Clinical Interest

There are no ECIs for this study.

8.4.8 Drug-device Combination Products/Combination Medicinal Products – Complaints, PQCs, and Malfunctions

The method of documenting and reporting complaints, PQCs, and malfunctions will occur as below and in Appendix 4. Refer to Appendix 7 for country-specific information and definitions.

To fulfill regulatory reporting obligations worldwide, medical device information associated with AEs will be collected and reported to the Sponsor in the same time frame as AEs per Section 8.4.1 via CRF (paper or electronic) and as per data entry guidelines.

PQCs/malfunctions, including those that involve a participant or any user/associated person, must be reported to the Sponsor. Sponsor shall review reported events by the investigator to fulfill the legal responsibility of notifying appropriate regulatory authorities and other entities about certain safety information relating to drug-device combination products/combination medicinal products being used in clinical studies.

The investigator is responsible for ensuring that follow-up includes any supplemental investigations as indicated to elucidate the nature and/or causality between the AE and the medical device or device constituent of combination product.

8.4.9 Adverse Events on the VRC

Participants/participant's legally acceptable representative will use an eVRC to report solicited and unsolicited AEs.

The definitions of solicited and unsolicited AEs can be found in Appendix 3.

8.4.9.1 Solicited Adverse Event

Solicited AEs for this study are summarized in [Table 3](#).

Table 3 Solicited Adverse Events for V116-013

Type of Solicited Adverse Event	Predefined Solicited Adverse Events (Preferred Term)	Solicited Period
Injection-site Adverse Event	
 • Injection-site pain or tenderness (injection-site pain) • Injection-site redness (injection-site erythema) • Injection-site swelling (injection-site swelling) 	Day 1 to Day 5 postvaccination
Systemic Adverse Event	
 • Muscle aches all over body (myalgia) • Headache (headache) • Tiredness (fatigue) • Hives or Welts (urticaria) • Irritability (irritability) • Joint pain (arthralgia) • Drowsiness (somnolence) • Feeling sick (malaise) 	Day 1 to Day 5 postvaccination
Note: Daily temperatures will be solicited Day 1 through Day 5 postvaccination. Elevated temperatures of $\geq 100.4^{\circ}\text{F}$ ($\geq 38.0^{\circ}\text{C}$) from Day 1 through Day 5 postvaccination will be categorized as solicited events of pyrexia.		

8.4.9.2 Unsolicited Adverse Events

Unsolicited AEs for this study are events that are 1) not predefined in [Table 3](#) or 2) predefined in [Table 3](#) but reported at any time outside the solicited period.

8.5 Treatment of Overdose

In this study, an overdose is any dose higher than 1 dose of study vaccine in any 24-hour period.

No specific information is available on the treatment of overdose.

8.6 Pharmacokinetics

Pharmacokinetic parameters will not be evaluated in this study.

8.7 Pharmacodynamics

Pharmacodynamic parameters will not be evaluated in this study.

8.8 Biomarkers

Biomarkers are not evaluated in this study.

8.9 Future Biomedical Research Sample Collection

All sample collections for study-specific assessments shown in the SoA are described within the main Informed Consent.

If the participant or participant's legally acceptable representative has provided documented informed consent/assent for FBR, leftover samples will be used for FBR. The following specimens will be included for FBR:

- Buccal swab DNA for future research

8.10 Medical Resource Utilization and Health Economics

Medical Resource Utilization and Health Economics are not evaluated in this study.

8.11 Visit Requirements

Visit requirements are outlined in Section 1.3. Specific procedure-related details are provided in Section 8.

8.11.1 Screening

Screening procedures will be conducted at Visit 1 as outlined in Section 1.3. Potential participants will be evaluated to determine that they fulfill the entry requirements as set forth in Section 5.

If Visit 1 is rescheduled (see Section 5.2), a pregnancy test (if applicable); a body temperature measurement; and a review of inclusion/exclusion criteria, prior medications/vaccinations, and medical history must be repeated before vaccination.

8.11.2 Treatment Period/Vaccination Visit

Requirements during the treatment period are outlined in Section 1.3. Participants are to be followed for at least 6 months after vaccination or until discontinuation from the study.

9 KEY STATISTICAL CONSIDERATIONS

This section outlines the statistical analysis strategy and procedures for the study; further details will be provided in the SAP. If, after the study has begun, but prior to any unblinding/final database lock, changes are made to primary and/or key secondary hypotheses, or the statistical methods related to those hypotheses, then the protocol will be amended (consistent with ICH Guideline E9). Changes to exploratory or other nonconfirmatory analyses made after the protocol has been finalized, but prior to any unblinding/final database lock, will be documented in the SAP and referenced in the CSR for the study. Post hoc exploratory analyses will be clearly identified in the CSR.

9.1 Responsibility for Analyses/In-house Blinding

The statistical analysis of the data obtained from this study will be the responsibility of the Clinical Biostatistics department of the Sponsor.

The study will be conducted as a double-blind study under in-house blinding procedures. The official final database will not be unblinded until medical/scientific review has been performed, protocol deviations have been identified, and data have been declared final and complete.

The Clinical Biostatistics department of the Sponsor will generate the randomized allocation schedule(s) for study intervention assignment. Randomization will be implemented in an IRT system.

Blinding issues related to the planned IAs are described in Section 9.6.

9.2 Hypotheses/Estimation

Objectives and hypotheses of the study are stated in Section 3 of the protocol.

9.3 Analysis Endpoints

Immunogenicity and safety endpoints will be evaluated for within- and/or between-intervention.

9.3.1 Immunogenicity Endpoints

Immune responses will be measured for all 21 serotypes contained in V116: 12 serotypes common to V116 and PPSV23 (3, 7F, 8, 9N, 10A, 11A, 12F, 17F, 19A, 20A, 22F, and 33F) and 9 serotypes unique to V116 (6A, 15A, 15C, 16F, 23A, 23B, 24F, 31, and 35B), and 2 cross-reactive serotypes (6C and 15B).

The primary immunogenicity endpoint includes:

- Serotype-specific OPA GMTs at 30 days postvaccination

The secondary immunogenicity endpoints include:

- Serotype-specific IgG GMCs at 30 days postvaccination
- Serotype-specific GMFR and proportion of participants with a ≥ 4 -fold rise from baseline (Day 1) to 30 days postvaccination for both OPA and IgG responses

The exploratory immunogenicity endpoints include the summaries of the cross-reactive immune responses to serotypes within a serogroup using serotype-specific OPA and IgG responses at 30 days postvaccination.

9.3.2 Safety Endpoints

Safety and tolerability will be assessed by clinical review of all relevant parameters, including AEs and vital signs.

The safety endpoints for overall safety assessment that address the primary objectives include:

- Proportion of participants with solicited injection-site AEs [redness (erythema), swelling (swelling), and pain or tenderness (pain)] from Day 1 through Day 5 postvaccination
- Proportion of participants with solicited systemic AEs [(muscle aches all over body (myalgia), headache (headache), tiredness (fatigue), hives or welts (urticaria), irritability (irritability), joint pain (arthralgia), drowsiness (somnolence), feeling sick (malaise), fever (pyrexia)] from Day 1 through Day 5 postvaccination. Note: Daily temperatures will be solicited Day 1 through Day 5 postvaccination. Elevated temperatures of $\geq 100.4^{\circ}\text{F}$ ($\geq 38.0^{\circ}\text{C}$) will be categorized as solicited events of pyrexia.
- Proportion of participants with vaccine-related SAEs from Day 1 through the duration of participation in the study

Additional safety endpoints for overall safety assessment include:

- Proportion of participants with the broad AE categories consisting of any AE, any unsolicited AEs, and any vaccine-related AE from Day 1 through Day 30 postvaccination
- Proportion of participants with the broad AE categories consisting of any SAE, any vaccine-related SAEs, and death from Day 1 through the duration of participation in the study. As this is a single-dose study, the broad AE category of discontinuation of study intervention due to an AE is not applicable
- Proportion of participants with maximum temperature measurements meeting the Brighton Collaboration cut points from Day 1 through Day 5 postvaccination

9.4 Analysis Populations

9.4.1 Immunogenicity Analysis Populations

The PP population will serve as the primary population for the immunogenicity endpoint(s). The PP population excludes participants due to important deviations from the protocol that

may substantially affect the results of the primary immunogenicity endpoint(s). Potential deviations that may result in the exclusion of a participant from the PP population include:

- Failure to receive study vaccine at Visit 1 (Day 1)
- Failure to receive correct clinical material as per randomization schedule
- Receipt of a prohibited medication or prohibited vaccine prior to study vaccination

Additional potential deviations that may result in the exclusion of a participant from the PP population for specific immunogenicity analyses (depending on the time point) include:

- Receipt of a prohibited medication or prohibited vaccine prior to a blood sample collection
- Collection of a blood sample outside the prespecified window

The final determination on important protocol deviations, and thereby the composition of the PP population, will be made prior to the final unblinding of the database and will be documented in a separate memo.

A supportive analysis using the FAS population will also be performed for the primary immunogenicity endpoint. The FAS population consists of all randomized participants who received at least 1 study vaccination and have at least 1 serology result. Participants will be included in the vaccination group to which they are randomized for the analysis of the immunogenicity data using the FAS population.

9.4.2 Safety Analysis Populations

Safety Analyses will be conducted in the APaT population, which consists of all randomized participants who received one dose of study intervention. Participants will be included in the vaccination group corresponding to the study vaccination they actually received for the analysis of safety data using the APaT population. This will be the group to which they are randomized except for participants who take incorrect study vaccination; such participants will be included in the group corresponding to the study vaccination actually received.

At least 1 temperature measurement obtained subsequent to study intervention is required for inclusion in the analysis of temperature.

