1.3 Schedule of Activities

Study Period:	Intervention and Follow-up					Notes
Visit Number:	1	2	3	4	5	
Visit Type:	Visit	TC	Visit	TC	TC	
Study Day:	Day 1	Day 7	Day 30	Day 90	Day 180	
Visit Window:	-	Day 7 to Day 10	Day 30 to Day 44	Day 76 to Day 104	Day 166 to Day 194	
Administrative Procedures						
Screening Procedures						
Informed Consent/Assent	X					Must be obtained before any study procedures are conducted.
Informed Consent/Assent for Optional FBR	X					Must be obtained before FBR sample collection.
Assignment of Screening Number	X					
Participant Identification Card	X					
Inclusion/Exclusion Criteria	X					
Medical History	X					
Postrandomization Procedures						
Assignment of Randomization Number	X					
Prior/Concomitant Medication and Nonstudy Vaccination Review	X	X	X	X	X	
V116/PPSV23 Administration (blinded)	X					
Provide Electronic Device (if needed) or Configure Device (Personal or Provisioned) for eVRC Data Collection	X					Instructions for using the eVRC will be reviewed with the participant or participant's legally acceptable representative.
Review eVRC Data With Participant or Participant's LAR		X	X			
Collect Electronic Device From Participant or Participant's Legally Acceptable Representatives Who Received an Electronic Device or Deactivate Personal Devices			X			
Complete Telephone Contact Questionnaire				X	X	
Safety Procedures						
Complete Physical Examination	X					Performed by investigator or medically qualified designee before vaccination.
Pregnancy Test (if applicable)	X					Participants of childbearing potential must have a negative urine or serum test (consistent with local requirements and sensitive to ≤ 25 IU hCG) result before vaccination.

Study Period:	Intervention and Follow-up					Notes
Visit Number:	1	2	3	4	5	
Visit Type:	Visit	TC	Visit	TC	TC	
Study Day:	Day 1	Day 7	Day 30	Day 90	Day 180	
Visit Window:	-	Day 7 to Day 10	Day 30 to Day 44	Day 76 to Day 104	Day 166 to Day 194	
Body Temperature Measurement	X					Measured before vaccination. Participants with febrile illness (temperature $\geq 100.4^{\circ}\text{F}$ [$\geq 38.0^{\circ}\text{C}$]) within 72 hours before vaccination must be rescheduled.
Postvaccination Observation Period	X					Observed by blinded study-site personnel for at least 30 minutes postvaccination.
AE Monitoring	X	X	X	X	X	Nonserious AEs collected through Day 30 postvaccination; all SAEs and deaths collected through Day 180.
Immunogenicity Assessments						

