8.1.10 Electronic Vaccination Report Card

The eVRC is structured as recommended in the final US FDA Patient-reported Outcome Guidance [U.S. Food and Drug Administration 2009].

The participant/participant's legally acceptable representative will use the eVRC to record body temperature (Section 8.3.4), solicited injection-site AEs, and solicited systemic AEs (Section 8.4.9.1). Unsolicited AEs (Section 8.4.9.2), concomitant medications, and nonstudy vaccinations (Section 8.1.5.2) will also be reported. The participant/participant's legally acceptable representative will be provided an electronic device or have their own electronic device configured, if compatible, to complete the eVRC. If the participant receives assistance completing the eVRC, all data reported on the eVRC must be entered as reported by the participant.

The investigator or qualified delegate will review the data captured on the eVRC with the participant/participant's legally acceptable representative as indicated in Section 1.3. Any changes to the data reported by the participant on the eVRC must be clearly explained in the participant's source documents.

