8.3.5 Postvaccination Observation Period

All participants will be observed for at least 30 minutes after vaccination for any immediate reactions. If any immediate AEs are observed during this period, the time at which the event occurred within this timeframe, as well as the event itself, any concomitant medications that were administered, and resolution of the event must be recorded on the appropriate eCRF.

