9.5.2.1 Overall Safety Assessment

The overall safety evaluation will include a summary by vaccination group (V116 group and PPSV23 group) of the number and percentage of participants with any AEs, any unsolicited AEs, any vaccine-related AEs, any SAEs, any vaccine-related SAEs, and any AEs resulting in death after vaccination. Point estimates and 95% CIs for the between-group differences (V116 compared with PPSV23) in the percentages of participants with the event will be provided for these events.

The number and percentage of participants with specific AEs will also be provided. Point estimates and 95% CIs for the differences between vaccination groups in the percentages of participants with specific AEs will be provided for solicited AEs and AEs that occur in $\geq 2\%$ of participants in the V116 group or PPSV23 group.

The number and percentage of participants with maximum temperature measurements meeting the Brighton Collaboration cut points [Marcy, S. M., et al 2004] will be provided along with point estimates and 95% CIs of between-group differences.

CIs for between-group differences will be provided using the M&N method [Miettinen, O. and Nurminen, M. 1985]. Rainfall plots with point estimates and 95% CIs will be displayed for AEs that occur in $\geq 5\%$ of participants in the V116 group or PPSV23 group.

A detailed analysis strategy for safety endpoints is listed in [Table 5](#).

Table 5 Analysis Strategy for Safety Parameters

Analysis Part	Safety Endpoint	Descriptive Statistics	Between-group 95% CI	Graphical Display
Overall Safety Assessment	Solicited injection-site AE (Day 1 through Day 5 postvaccination) ^a	X	X	
	Solicited systemic AE (Day 1 through Day 5 postvaccination) ^a	X	X	
	Any AE ^b	X	X	
	Any unsolicited AE ^b	X	X	
	Any vaccine-related AE ^b	X	X	
	Any SAE ^b	X	X	
	Any vaccine-related SAE ^b	X	X	
	Death ^b	X	X	
	Specific AEs by SOC and PT ^c	X	X	X
Maximum temperatures (Day 1 through Day 5 postvaccination) ^d	X	X		

AE=adverse event; CI=confidence interval; PT=preferred term; SAE=serious adverse event; SOC=system organ class.

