9.8.2 Sample Size and Power for Safety Analyses

The probability of observing at least 1 SAE in this study depends on the number of participants vaccinated and the underlying incidence of participants with an SAE in the study population. The sample size was selected to achieve a reasonably sized safety database exposed to V116. Calculations below assume that 100% of randomized participants will be evaluable for safety analyses.

There is 80% probability of observing at least 1 SAE among 492 participants in the V116 group if the true incidence rate is 0.33% (1 of every 306 participants receiving the vaccine). There is a 50% probability of observing at least 1 SAE among 492 participants in the V116 group if the true incidence rate is 0.14% (1 of every 710 participants receiving the vaccine). If no SAEs were observed among 492 participants, this study will provide 97.5% confidence that the underlying percentage of participants with an SAE is <0.75% (1 out of every 133 participants) in the V116 group.

The percentage point differences between the 2 vaccination groups that could be detected with 80% probability are summarized in [Table 6](#) for a variety of hypothetical underlying incidences of an AE.

Table 6 Differences in Incidence of Adverse Event Rates Between the 2 Vaccination Groups That Can be Detected With an Approximately 80% Probability

Incidence of an Adverse Event		Risk Difference
V116 (%) N=492	PPSV23 (%) N=328	Percentage Points
2.4	0.1	2.3
6.0	2.0	4.0
10.4	5.0	5.4
16.9	10.0	6.9
22.9	15.0	7.9
28.6	20.0	8.6
39.5	30.0	9.5

Incidences presented here are hypothetical and do not represent actual adverse experiences in either group. The incidences assume a 2-sided 5% alpha-level with 492 participants in the V116 group and 328 participants in the PPSV23 group. No multiplicity adjustments were made. Based on an asymptotic method proposed by Farrington and Manning (1990) [Farrington, C. P. and Manning, G. 1990]

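### Solicited reaction rates are taken over all vaccinated children, so a child with no Day 1–5 report-card data counts as a non-reactor; the effect is descriptive and probably small

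*Combined protocol and SAP*

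**What the plan says.** Section 9.4.2 states: "Safety Analyses will be conducted in the APaT population, which consists of all randomized participants who received one dose of study intervention". It then sets one data condition: "At least 1 temperature measurement obtained subsequent to study intervention is required for inclusion in the analysis of temperature".

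Section 9.3.2 lists three endpoints for the primary safety objective. The first begins "Proportion of participants with solicited injection-site AEs", the second is its systemic counterpart, and both cover Day 1 through Day 5. The third is vaccine-related SAEs and does not depend on the electronic vaccination report card (eVRC).

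Section 9.5.2.1 says "A detailed analysis strategy for safety endpoints is listed in" Table 5. Neither that table nor its footnotes give another denominator or a missing-data rule for solicited events. Table 4, for immunogenicity, has a missing-data column, and the full analysis set in Section 9.4.1 requires a serology result.

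Section 10.3.2 defines solicited events as predefined events that the participant or representative is asked about and enters on the report card. Section 9.8.2 says of its own figures: "Calculations below assume that 100% of randomized participants will be evaluable for safety analyses". Section 9 defers further detail to an SAP, and the supplied text contains no separate rule on this point.

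**The concern.** Temperature and solicited reactions are recorded on the same eVRC over the same five days. A child whose family enters nothing is left out of the temperature analysis but kept in the solicited-event analysis. Read with the definition in Section 10.3.2, that child cannot have a solicited event, so missing data are silently treated as no reaction.

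Within an arm this can lower the reported rate but not raise it. Between arms, equal missingness shrinks a true difference slightly, and unequal missingness can move it either way.

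Pyrexia adds an uncertainty. It is derived from temperature, yet Section 9.3.2 counts it as a solicited systemic event, so the text leaves open whether its denominator follows the temperature condition or all vaccinated children.

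**Working it through.** **Inputs from the plan.** 492 children on V116 and 328 on PPSV23; the Table 6 rates; 95% confidence intervals by Miettinen and Nurminen (M&N).

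**Assumptions.** No expected share without data is given. I take *m*, the share with no Day 1–5 eVRC data, as 1%, 2% or 5%, and an overall reaction rate *p* of 60%. *r* is the share of such children's reactions that is counted from another source, and *q* is their true reaction rate.

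**The plan's own figures.** Power for two proportions with pooled null variance and a two-sided 5% level gives 80.5, 80.5, 80.3, 80.5, 80.4, 80.1 and 79.9% for the seven rows of Table 6. The SAE statements also reproduce: 1 − (1 − 1/306)^492 = 80.0%, 1 − (1 − 1/710)^492 = 50.0%, and 1 − 0.025^(1/492) = 0.747%. Nothing in Section 9.8.2 is wrong on its stated assumptions.

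**One arm, non-reporters like reporters.** Reported rate = p × (1 − m(1 − r)).

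| m | about n of 492 | r = 0 | r = 0.5 | r = 1 |
|---|---|---|---|---|
| 1% | 5 | 59.4% | 59.7% | 60.0% |
| 2% | 10 | 58.8% | 59.4% | 60.0% |
| 5% | 25 | 57.0% | 58.5% | 60.0% |

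With r = 0 the understatement is 0.6, 1.2 or 3.0 points. For scale, the 95% half-width for 60% of 492 is 1.96 × √(0.6 × 0.4/492) = 4.3 points.

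**Between arms, last row of Table 6, r = 0.** Reported difference = 39.5(1 − mV) − 30.0(1 − mP), where mV and mP are the missing shares on V116 and PPSV23.

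| mV | mP | Difference (points) | M&N 95% CI |
|---|---|---|---|
| 0 | 0 | 9.5 | 2.8 to 16.0 |
| 1% | 1% | 9.4 | |
| 2% | 2% | 9.3 | |
| 5% | 5% | 9.0 | |
| 1% | 2% | 9.7 | |
| 2% | 1% | 9.0 | |
| 1% | 5% | 39.11 − 28.50 = 10.6 | 4.0 to 17.0 |
| 5% | 1% | 37.53 − 29.70 = 7.8 | 1.2 to 14.3 |

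With equal true rates of 30%, 50% or 70%, and 5% missing on V116 against 2% on PPSV23, the false difference is −0.9, −1.5 or −2.1 points. The sign reverses if the missing shares are swapped.

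**When the remedy is worse.** If non-reporters react at rate q and the overall rate is p, the all-vaccinated rate is too low by mq(1 − r). The rate among children with data is (p − mq)/(1 − m), which differs from p by m(p − q)/(1 − m). For q below p, the two errors are equal at q = p/(1 + (1 − r)(1 − m)). With p = 60% and m = 5% this is 30.8% for r = 0 and 40.7% for r = 0.5. If non-reporters never react, the diary-based rate is 60.6%, 61.2% or 63.2% at m = 1%, 2% or 5%, while the all-vaccinated rate is the correct 60.0%.

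**The case against.** The plan does state a denominator, and Section 9 leaves detail to the SAP. A maximum temperature cannot be categorised without a reading, whereas adverse events reach the database by several routes. Section 8.3.5 provides for recording on the eCRF "If any immediate AEs are observed during this period" (the 30-minute observation). The schedule has "Review eVRC Data With Participant" at Visits 2 and 3, and Section 8.1.10 allows for corrections ("Any changes to the data reported by the participant on the eVRC must be clearly explained"). Sites also report nonserious events through Day 30. Few children may end with no Day 1–5 information, and if every missed reaction is recovered, the all-vaccinated rate is exact.

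Much of this stands. The number affected may be small, and which denominator is closer to the truth depends on q, r and m, none of which is known. That argues for showing both. High recovery outside the eVRC carries less weight: under Section 10.3.2 a reaction recorded only by the site is not a solicited event. It would count as unsolicited and under any AE, so a data condition for solicited events would not lose it from the safety analysis.

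A reader might infer that the plan tilts the comparison in favour of V116. The documents do not support that. Shifts above 1 point within the range examined need clearly unequal missingness, such as 5% against 1%. No document suggests this, and families and the staff who evaluate the children are blinded.

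**Conclusion.** The gap is real and narrow. Two of the three primary safety endpoints use a denominator that treats children without Day 1–5 eVRC data as non-reactors, while the same section protects the temperature analysis from this. With an assumed 60% rate and no recovery, the understatement is 0.6 to 3.0 points for 1% to 5% missing, if non-reporters resemble reporters. Equal missingness of 5% moves the Table 6 difference by about half a point.

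A reader might go further and conclude that a hypothesis test, the sample size or Table 6 is affected. They are not: safety is estimated without a test, and Table 6 reproduces on its stated assumption of full evaluability. Vaccine-related SAEs are untouched.

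A reader might also compare Section 8.4.9.2 with Table 9 and conclude that reactions first mentioned at the Day 7–10 call will be misclassified. Table 9 is an intensity scale and does not settle this. The wording that needs reconciling is between Section 8.4.9.2, which turns on when a predefined event is reported, and Section 10.3.2, which turns on whether it was entered on the report card. That is a separate clarification.

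**What to change.** In Section 9.4.2, next to the temperature sentence:

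- Admit a participant to the solicited-event analysis only with at least one Day 1–5 eVRC response on solicited events. Reaction and no reaction both qualify, including days completed at the Visit 2 or 3 review.
- Report the number without such data in each arm.
- Keep the all-vaccinated percentages as a sensitivity table.
- Leave SAEs, deaths, unsolicited AEs and any AE in the all-vaccinated population.
- State whether pyrexia follows the temperature condition or the solicited-event condition.

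Separately, reconcile Section 8.4.9.2 with the definition in Section 10.3.2.

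The cost is a few sentences and one table. Denominators fall slightly: at 5% missing, V116 goes from 492 to about 467. The diary-based rate is too high if non-reporters reacted much less often than reporters. With no recovery, the all-vaccinated rate is the closer one when their rate is below about half the overall rate, which is why both tables are needed. A child with one completed day would still count as observed, so partly completed diaries are only partly addressed.
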